Active Investigational Product: AAV5-hFVIII-SQ IND/European Union Drug 2017-003215-19 Regulating Authorities Clinical Trials (EudraCT) Number: ND #: 017659

Indication: Hemophilia A

Sponsor: BioMarin Pharmaceutical Inc.

[name] [name]

Development Phase: Phase 3

Sponsor's Responsible Medical

Monitor:

PI , MD, PhD

BioMarin Pharmaceutical Inc.

[name] [name]

Duration of Subject Approximately 264 weeks

Participation:

Dose: 6E13 vg/kg

Study Population: Males aged 18 or older

Date of Original Protocol: 14 August 2017

Date of Amendment 1 (United 2 October 2017

States Specific):

Date of Amendment 1 (Global) 25 January 2018
Date of Amendment 2 (Global) 28 June 2018
Date of Amendment 3 (Global) 24 August 2018
Date of Amendment 4 (Global) 9 November 2018

Date of Amendment 5 (Global) 10 May 2019 (unreleased)

Date of Amendment 6 (Global) 3 April 2020
Date of Amendment 7 (Global) 14 July 2021
Date of Amendment 7 (US) 15 July 2021

Property of BioMarin
CONFIDENTIAL

May not be divulged, published, or otherwise disclosed to others without prior written approval from BioMarin.

This study will be conducted according to the principles of Good Clinical Practice as described in the U.S. Code of Federal Regulations and the International Conference on Harmonisation Guidelines, including the archiving of essential documents

CLINICAL STUDY PROTOCOL AMENDMENT SUMMARY

Amendment 7 (United States-Specific)

Date: 15 July 2021

RATIONALE AND SUMMARY OF CHANGES

A summary of major changes covered by Amendment 7 to the 270-**301 prot**ocol is provided below.

1. Changes have been made to enhance screening for potential malignancies (including hepatic cancers) after dosing with BMN 270.

Rationale: The changes made include:

- Including a targeted liver ultrasound at the End of Year visits for Year 2 through Year 5 to screen for HCC (additional interim liver ultrasounds may be performed at the discretion of the Investigator);
- Recommending genomic analyses for any malignancy (except non-melanoma skin cancer) diagnosed during the course of the study.

Year-end liver ultrasounds are being implemented to assess the theoretical risk of HCC. While no cases of HCC have been reported in the Sponsor's AAV gene therapy non-clinical or clinical trials (more than 150 patients dosed, with some dosed more than 5 years ago), these assessments will further inform this theoretical risk.

 Malignancy (except non-melanoma skin cancer) has been added as an Event of Special Interest (EOSI).

Rationale: The occurrence of malignancy (as above) was added as an EOSI for purposes of expedited safety reporting and additional safety monitoring.

3. Language around the statistical analysis of secondary endpoints and objective has been amended.

Rationale: The efficacy evaluation period for analysis of the secondary endpoints (annualized bleeding rate and exogenous FVIII usage) has been changed to examine the period from Week 5 to the last visit at the time of any data cutoff (as opposed to the original language, which was from Week 5-Week 52). This change reflects the plan to extend the timeframe of the study and allow for the possibility of producing one or more interim CSRs that may have data cutoffs after Week 52 but before the end of the study (Week 260).

4. Language has been added concerning the use of the SARS-CoV-2 vaccines.

Rationale: Due to the current worldwide SARS-CoV-2 pandemic and evolving availability and types of vaccines, language has been added to assist with timing and planning for **vaccine administration**. **The Sponsor's recommendations reflect the risk** assessment conducted on the currently available vaccines and guidance from multiple health agencies, and include information regarding different types of SARS-CoV-2 vaccines.

5. The reactive corticosteroid regimen for ALT elevation has been updated.

Rationale: The guidance for the reactive corticosteroid regimen, including management of ALT elevations and corticosteroid taper, reflects the data gathered from previous BMN 270 studies. This change attempts to promote the safe and effective use of reactive corticosteroids.

Thrombin generation assay (TGA) assessment has been removed.

Rationale: Assessment of TGA to date in the BMN 270 development program has provided sufficient data; additional assessments are not expected to be needed. Removing this assessment helps to alleviate patient and site burden. If TGA assessments from 270-301 are needed in the future, backup aliquots from other platelet-poor plasma samples may be utilized.

7. The definition of treatment failure has been changed.

Rationale: The previous definition required either a failure to achieve FVIII activity ≥ 5 IU/dL by Week 52 or an inability to maintain independence from prophylactic FVIII replacement therapy due to joint bleeding episodes; the revised definition requires both of these conditions to be present before a subject may be considered a treatment failure. The revision reflects the data seen as of the 52-week data cut for 270-301, where some subjects were still able to remain off of prophylactic FVIII replacement therapy (due to an absence of treated bleeding events) despite lower FVIII levels 1 or more years after BMN 270 infusion.

- **8.** Frequency of several laboratory assessments during Years 2-5 has been decreased. These changes include:
 - Reducing FVIII Antigen BDD Assay to Q12W for Years 2-5
 Rationale: Robust characterization is already available from Year 1 data, and more frequent sampling is not needed to understand long-term protein to activity ratios
 - Reducing AAV5 TAb to End of Year Visits only for Years 3-5
 Rationale: Antibody response is high and does not change much over time. Yearly testing should be sufficient to understand longer term responses, as little change is expected.

Page 4

- Reducing FVIII TAb to End of Year Visits only for Years 3-5
 - Rationale: FVIII Bethesda Inhibitor is the main safety assessment. After 3 years, if there is a need in specific instances for data more frequent than once a year, backup plasma from another assay may be used for testing.
- Reducing AAV5 TI assay to End of Year 5 Visit only (or at the Early Termination Visit, as applicable)
 - Rationale: The most significant information from this assessment is obtained from baseline and samples collected shortly after dosing. As the TI remains high after dosing, there is no need to continue to track frequently beyond a year after infusion.
- **9.** Additional changes to the statistical analysis language have been made, including a new protocol appendix that outlines changes made specifically for analyses to be submitted in **the United States.**

Rationale: The changes were made in alignment with the FDA's request to revise this protocol and the statistical analysis plan (SAP) to specify annualized bleeding rate (ABR) as the primary endpoint, with the primary efficacy assessment based on results through two years post-BMN 270 infusion follow-up for all subjects.

- **10.** Additional details on obtaining multiple biopsies as part of the liver biopsy substudy have been added.
- 11. The identity of the medical monitor has been updated.
- 12. Minor changes have been made for purposes of consistency and clarity.

Refer to Section 26 for a summary of revisions to Amendment 6 (dated 3 April 2020).

Page 5

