	bleeding, infection, and injury to nearby organs, are very rare, but the subject will be monitored appropriately to ensure correct	
	management should any of these occur. Any complications related to the liver biopsy should be reported as adverse events, as outlined in Section 10. The liver biopsy is a standard investigation, and will be explained more fully by the experienced clinician	
	performing the biopsy.	
	performing the biopsy.	
	Each subject who participates in this optional sub-study will have a comprehensive pre-/post-biopsy surveillance plan according to	
	the standard procedures at the institution. Timing of the liver biopsies will occur at Weeks 26, 52, and/or during Years 2-5. Safety	
	will be assessed by adverse event reporting and clinical laboratory assessments. Per the Investigator's discretion and/or according to	
	local guidelines, the subject may be kept in overnight following the liver biopsy for additional safety monitoring; such an overnight	
	stay would not be considered a hospitalization for serious adverse event (SAE) reporting purposes (refer to Section 10.4.1.7).	
	There is no direct benefit from participating in this study other than contributing to understanding the mechanism of action of	
	BMN 270. Consenting into this specific sub-study is optional and will not have any effect on the subject's continued participation in	
	270-301.	
Section 8/Study	The exploratory objectives of the liver biopsy substudy are:	10
Objectives	• To examine the histopathology of the liver following BMN 270 therapy, including assessing for possible safety findings	
	(eg, fibrosis, fatty liver disease, lymphocytic invasion)	
	To quantify FVIII DNA, RNA, and protein expression within hepatocytes	
	 To determine which forms of rAAV vector DNA are present at the time of biopsy. 	
	To determine the transduction pattern of BMN 270 in humans (ie, peri-portal hepatocytes, central vein hepatocytes)	
g .: 0.1/0 11	An interim analysis is planned after 20 treated HIV-negative subjects have completed the Week 26 visit. Two interim analyses were	1 2 10 12
Section 9.1/Overall Study Design and Plan	planned, after the first approximately 16 and 20 treated HIV-negative subjects, respectively, completed the Week 26 visit (or have	1, 3, 10, 12
Study Design and I fan	discontinued study participation prior to Week 26). The first interim analysis was performed as planned in May 2019. Based on the	

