7.4.1 Optional Liver Biopsy Substudy Risks and Benefits

Liver biopsy is considered a safe procedure, with serious complications occurring less than once in every 10,000 procedures (Grant 2004). Although the theoretical risks of significant complications are extremely small, the main complications would include bleeding and bile leakage. Another theoretical complication is infection at the needle insertion site; the sterile technique used makes this risk extremely small.

The most common problems include mild pain and a minor decrease in blood pressure. More serious complications, such as bleeding, infection, and injury to nearby organs, are very rare, but the subject will be monitored appropriately to ensure correct management should any of these occur. Any complications related to the liver biopsy should be reported as adverse events, as outlined in Section 10. The liver biopsy is a standard investigation, and will be explained more fully by the experienced clinician performing the biopsy.

Each subject who participates in this optional substudy will have a comprehensive pre-post-biopsy surveillance plan according to the standard procedures at the institution.

Timing of the liver biopsies will occur at Weeks 26, 52, and/or during Years 2-5. Safety will be assessed by adverse event reporting and clinical laboratory assessments. Per the

Investigator's discretion and/or according to local guidelines, the subject may be kept in

270-301 Amendment 7 (United States Specific)

Page 38

overnight following the liver biopsy for additional safety monitoring; such an overnight stay would not be considered a hospitalization for serious adverse event (SAE) reporting purposes (refer to Section 10.4.1.7).

There is no direct benefit from participating in this study other than contributing to understanding the mechanism of action of BMN 270. Consenting into this specific substudy is optional and will not have any effect on the subject's continued participation in 270-301.

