10.1.1.1 Bleeding and Suspected Bleeding Events

All bleeding events and suspected bleeding events, regardless of the need for exogenous FVIII therapy as treatment, should be captured in subject diaries and recorded on the designated bleeding eCRF. Bleeding events and suspected bleeding events should not be reported as adverse events, with the following exception:

All bleeding events and suspected bleeding events which meet one or more of the
criteria for being serious (refer to Section 10.2) should be reported as serious adverse
events (whether or not they are bleeding events that are normal sequelae of
hemophilia, and whether or not they required exogenous FVIII as treatment).

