10.4.1.7 Hospitalization, Prolonged Hospitalization, or Surgery

Any AE that results in hospitalization or prolonged hospitalization should be documented and reported as an SAE unless specifically instructed otherwise in this protocol (refer to Section 10.2).

There are some hospitalization scenarios that do not require reporting as an SAE when there is no occurrence of an AE. These scenarios include planned hospitalizations or prolonged hospitalizations to:

Perform a protocol-mandated efficacy measurement

- Undergo a diagnostic or elective surgical procedure for a pre-existing medical condition that has not worsened
- Insert an in-dwelling IV catheter (such as a Port-a-Cath or other brand, if applicable) for administration of study drug or FVIII replacement therapy
- Receive scheduled therapy (study drug or otherwise) for the study indication

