25.2 Region-Specific Study Endpoints

- Primary efficacy endpoint
 - Change from baseline (prior to BMN 270 infusion while receiving FVIII prophylaxis) in the annualized number of bleeding episodes requiring exogenous FVIII replacement treatment (annualized bleeding rate, ABR) in the efficacy evaluation period ("Week 5 to Last Visit")
- Secondary efficacy endpoints
 - Change from baseline (assuming no treatment for severe hemophilia A) in FVIII activity, as measured by chromogenic substrate assay, at Week 104 post-BMN 270 infusion
 - Change from baseline (prior to BMN 270 infusion while receiving FVIII prophylaxis) in the annualized utilization (IU/kg/year) of exogenous FVIII replacement therapy in the efficacy evaluation period ("Week 5 to Last Visit")
- Tertiary efficacy endpoints
 - Change from baseline in the total score of Haemo-QoL-A at Week 104 of the study post-BMN 270 infusion
 - Change from baseline in the EQ-5D-5L score at Week 104 of the study post-BMN 270 infusion
 - Change from baseline in the HAL score at Week 104 of the study post-BMN 270 infusion
 - Change from baseline in the WPAI+CIQ:HS score at Week 104 of the study post-BMN 270 infusion
 - Change from baseline in PROBE score at Week 104 of the study post BMN 270 infusion

- Safety endpoints
 - Incidence of AEs and SAEs
 - Change in clinical laboratory tests (serum chemistry and hematology)
 - Change in vital signs
 - Change in physical examination
 - Vector shedding (blood, urine, semen, stool, saliva)
 - Liver tests (LTs, including ALT, AST, GGT, direct and total bilirubin, LDH, and alkaline phosphatase)
 - o Immune response to FVIII transgene product and AAV5 capsid proteins

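### A non-serious bleed after the optional liver biopsy is an adverse event under Section 7.4.1 but barred from adverse event reporting by Section 10.1.1.1

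*Protocol*

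**What the plan says.** Section 7.4.1 (Optional Liver Biopsy Substudy Risks and Benefits) is the current statement of biopsy risk; the Amendment 6 revision table carries the same text. On complications it says "the main complications would include bleeding and bile leakage", and it puts bleeding first again when it lists the more serious ones. Its reporting instruction is "Any complications related to the liver biopsy should be reported as adverse events, as outlined in Section 10". It then says that safety will be judged from AE reports and clinical laboratory results. It also deals with precautionary overnight observation: an overnight "stay would not be considered a hospitalization for serious adverse event (SAE) reporting purposes (refer to Section 10.4.1.7").

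Section 10.1.1.1 sets the study-wide rule for bleeds. Every bleed or suspected bleed, treated or not, goes into the diary and onto a dedicated bleeding eCRF. For AE purposes, "Bleeding events and suspected bleeding events should not be reported as adverse events, with the following exception": a bleed that meets at least one seriousness criterion in Section 10.2 is reported as an SAE, whether or not it is a usual consequence of hemophilia.

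Section 10.4.1.7 introduces its exempt hospital stays with "There are some hospitalization scenarios that do not require reporting as an SAE when there is no occurrence of an AE".

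**The concern.** The two sections give opposite instructions for one kind of event: a non-serious bleed caused by the biopsy. The cross-reference in Section 7.4.1 does not settle the matter, because the section it cites contains the prohibition.

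At stake is how a recognized harm of an invasive research procedure is reported in people with a bleeding disorder. Section 7.4.1 says that taking part brings them no direct benefit, and Section 9.7.7.1 allows more than one biopsy. If some sites follow Section 7.4.1 and others Section 10.1.1.1, the AE incidence for biopsy bleeding mixes two definitions. If all follow Section 10.1.1.1, AE tables that Section 7.4.1 presents as the basis for judging biopsy safety will contain no non-serious biopsy bleeds, however many occur.

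**Working it through.** The plan states no figure to reproduce and no formula applies. The check sets the rules side by side, class by class.

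| Event after biopsy | Section 7.4.1 | Section 10.1.1.1 | Agreement |
|---|---|---|---|
| Bleed meeting a seriousness criterion | Reported, through Section 10 | SAE | Yes |
| Bleed meeting no seriousness criterion | AE | Not an AE; diary and bleeding eCRF only | No |
| Bile leakage, infection, pain, organ injury | AE | Not covered; ordinary AE rules apply | Yes |

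The conflict is confined to the second row. Three further checks show whether anything else in the protocol resolves it.

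1. *Is Section 10.1.1.1 limited to bleeds from the disease?* No. Its exception explicitly spans bleeds that are, and bleeds that are not, usual consequences of hemophilia. Bleeds of other origin were therefore in view, and only serious ones were let through. There is no carve-out for procedures.

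2. *Does either section take precedence?* The protocol does not say. Its precedence clause (Sections 14.10 and 25.3.1) concerns statistical methods in the SAP against the protocol. If Section 10 governs, the instruction that any complication is an AE is untrue for non-serious bleeds. If Section 7.4.1 governs as the more specific text, the single exception in Section 10.1.1.1 is incomplete.

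3. *Does another stated safety output pick these bleeds up?*
   - The safety endpoints in Section 25.2 and the safety analyses in Sections 14.7 and 25.3.6 list AEs and SAEs, laboratory tests, vital signs, physical examination, vector shedding and immune response. Bleeding eCRF entries are not among them.
   - The separate substudy report in Section 14.4 covers the exploratory objectives in Section 8. These concern liver histology, vector DNA, expression and transduction pattern, not harm from the procedure.
   - Section 9.7.7.1 sends clinically significant histopathology findings to AE reporting; it does not address procedural bleeding.

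Under Section 10 as written, a non-serious biopsy bleed is therefore recorded on the bleeding eCRF and appears in none of the safety outputs that the protocol names.

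**The case against.** The strongest reply is that little is lost. Section 7.4.1 is background on risk and defers to Section 10. Serious biopsy bleeds are SAEs under both sections. Non-serious ones are still collected on the bleeding eCRF, so they are displaced rather than missing. The substudy is optional and exploratory, and its eligibility criteria require a minimum documented FVIII activity shortly before the procedure. All of this stands. It limits the size of the point but leaves the contradiction: deferring to Section 10 produces the opposite of what Section 7.4.1 says, for an event that Section 7.4.1 says will be judged through AE reports.

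Three stronger readings are tempting, and the documents do not support them.

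- *The main biopsy risk disappears from the AE data.* It does not. Section 7.4.1 names bleeding in the context of significant and more serious complications, and bleeds that meet a seriousness criterion remain in the SAE data.

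- *A bleed kept overnight loses its only route to SAE reporting.* The overnight sentence concerns precautionary observation, not a stay to treat a bleed. It refers to Section 10.4.1.7, which carries the condition that no AE has occurred. The list there is introduced as inclusive, so the absence of this stay from it proves nothing. Hospitalization is also only one criterion: life-threatening events and important medical events remain in Section 10.2, which also makes a complication serious if it prolongs hospitalization. What survives is that Section 7.4.1 could repeat the no-AE condition.

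- *Procedure-caused bleeds distort the bleeding-rate endpoint.* A treated biopsy bleed is not expressly excluded from ABR, but the effect is negligible. For illustration, take Weeks 5 to 104: 100/52 = 1.92 years; one extra bleed adds 1/1.92 = 0.52 per year for that subject, and 0.52/110 = 0.0047 to a 110-subject mean, against a margin of 3.5. The actual period runs to each subject's last visit before the cutoff, so subjects followed beyond Week 104 contribute less. Supportive analyses are left to the SAP, so no extra ABR analysis is called for here.

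**Conclusion.** The point holds in its narrow form. Sections 7.4.1 and 10.1.1.1 contradict each other on whether a non-serious biopsy-related bleed is an AE, and following Section 10 keeps such bleeds out of the AE tables. Confidence is high, because this follows directly from the wording of the two sections.

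The number of events cannot be computed. The protocol gives neither how many subjects will have a biopsy nor how often a non-serious bleed follows one. The figure it cites, fewer than one in 10,000 procedures, is for serious complications and says nothing about this class. What can be said is that all non-serious biopsy bleeds count as AEs under one section and none do under the other.

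This is a defect in safety reporting, modest in scale. It touches no hypothesis test, margin, sample size or error rate. It is a protocol matter rather than SAP detail, because it determines what sites enter on the AE form.

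**What to change.** Reconcile the two sections. In Section 10.1.1.1, add a second exception: bleeding related to the study liver biopsy is recorded as an AE, or as an SAE if it meets a seriousness criterion, in addition to its entry on the bleeding eCRF. Section 7.4.1 then agrees with the section it cites.

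As a minor clarification, state in Section 7.4.1 that the overnight-stay exemption applies only where no AE has occurred, in line with Section 10.4.1.7.

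The cost is two short text changes and a few more non-serious AEs to report. No change to the ABR analysis is needed.

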2 SYNOPSIS

NAME OF COMPANY BioMarin Pharmaceutical Inc. [name] [name]	Referring to Part of the Dossier:	FOR NATIONAL AUTHORITY USE ONLY:
	Volume:	
NAME OF FINISHED PRODUCT: BMN 270	Page:	
NAME OF ACTIVE INGREDIENT: AAV5-hFVIII-SQ	Reference:	

TITLE OF STUDY:

A Phase 3 Open-Label, Single-Arm Study To Evaluate The Efficacy and Safety of BMN 270, an Adeno-Associated Virus Vector—Mediated Gene Transfer of Human Factor VIII in Hemophilia A Patients with Residual FVIII Levels ≤ 1 IU/dL Receiving Prophylactic FVIII Infusions

PROTOCOL NUMBER:

270-301

STUDY SITES:

Approximately 60 sites worldwide.

PHASE OF DEVELOPMENT:

Phase 3

STUDY RATIONALE:

Hemophilia A (HA) is an X-linked recessive bleeding disorder that affects approximately 1 in 5,000 males. It is caused by deficiency in the activity of coagulation factor VIII (FVIII), an essential cofactor in the intrinsic coagulation pathway. This disorder can be either inherited, due to a genetic aberrancy, or an acquired immunologic process, leading to insufficient quantities of FVIII or a dysfunctional FVIII, but all are characterized by a defective coagulation process. The clinical phenotype of HA patients generally correlates tightly with the level of residual expression. Severe HA is classified as FVIII activity less than 1% of wild-type (< 1 IU/dL), moderate disease comprises 1-5% of wild-type activity and the mild form is 5-40% activity. The clinical manifestations of severe HA are frequent spontaneous bleeding episodes, predominantly in joints and soft tissues, with a substantially increased risk of death from hemorrhage when the brain is involved. Subjects with moderate disease can exhibit manifestations similar to those seen in patients with severe HA, resulting in a comparable bleeding phenotype. Treatment of severe HA presently consists of intravenous injection of plasma-derived or recombinant human FVIII protein (rhFVIII) concentrates, both as prophylaxis 2³ times per week, and at the time of a bleed, to prevent or control bleeding episodes, respectively. The half-life for FVIII (12 to 18 hours for most approved products) necessitates frequent infusions, and although a major advance in the treatment of HA, it remains common for severe HA patients to continue to have multiple bleeding events on prophylactic therapy (median annualized bleeding rate [ABR] of 1 4 with prophylaxis treatment in a recently published retrospective observational study and between 1.2 in 6 prospective FVIII interventional studies) and on demand-only therapy (median ABR of 4.5-18 in a recently published retrospective study and between 20-60 in 6 prospective FVIII interventional studies). The consequence of multiple bleeding events is the development of

Page 6

NAME OF COMPANY BioMarin Pharmaceutical Inc. [name] [name]	SUMMARY TABLE Referring to Part of the Dossier:	FOR NATIONAL AUTHORITY USE ONLY:
NAME OF FINISHED PRODUCT:	Volume:	
BMN 270	Page:	
NAME OF ACTIVE INGREDIENT: AAV5-hFVIII-SQ	Reference:	

debilitating multiple-joint arthropathy and substantially increased risk of death. Chemical modification (eg, direct conjugation of polyethylene glycol (PEG) polymers) and bioengineering of FVIII (eg, FVIII-Fc fusion proteins) improve half-life by approximately 50%, and thus, show promise in reduced dosing and maintaining activity levels above a 1% trough for a greater proportion of the dosing interval. However, patients with severe HA who are treated with extended half-life FVIII remain dependent on multiple infusions to maintain critical levels of FVIII activity. There is therefore a strong unmet need for a fully preventive treatment of HA to give patients a FVIII level compatible with a normal and hemorrhage-free life.

Gene therapy offers the potential of disease-modifying therapy by continuous endogenous production of active FVIII following a single intravenous infusion of a vector encoding the appropriate gene sequence for long-term episomal expression. Hemophilia A is well-suited for a gene replacement approach because clinical manifestations are attributable to the lack of a single gene product (FVIII) that circulates in minute amounts (200 ng/ml) in the plasma. Tightly regulated control of gene expression is not essential, and even modest increases in the level of FVIII (any increase of the plasma level by 2 ng/ml induces an increase in activity of 1%) can ameliorate the severe form of hemophilia A. Thus, relatively small changes in endogenous FVIII activity can result in clinically relevant improvements in disease phenotype. Finally, the circulating FVIII response to gene transduction can be assessed using validated quantitative rather than qualitative endpoints that are easily assayed using established laboratory techniques.

Several different gene transfer strategies for FVIII replacement have been evaluated, but adeno-associated viral (AAV) vectors show the greatest promise. They have an excellent and well-defined safety profile, and can direct long-term transgene expression with tropism and

promoter specificity for specific tissues, such as the liver (for serotypes 2, 5 and 8 among others). Indeed, an ongoing gene therapy clinical trial for a related disorder, hemophilia B, has established that stable (median follow-up of 3.2 years) excression of human factor IX (hell) at levels that are

that stable (median follow-up of 3.2 years) expression of human factor IX (hFIX) at levels that are sufficient for conversion of their bleeding phenotype from severe to moderate or mild is achievable

following a single peripheral vein infusion of AAV8-hFIX vector. Several participants in this trial have been able to discontinue factor prophylaxis without suffering spontaneous hemorrhages, even

when they undertook activities that previously resulted in bleeding. Thus, gene therapy treatment has resulted in a substantial improvement in their quality of life.

BMN 270 is an AAV5-based gene therapy vector that expresses the SQ form of hFVIII under the control of a hybrid human liver-specific promoter (Figure 1).

NAME OF COMPANY

[name]

[name]

BioMarin Pharmaceutical Inc.

270-301 Amendment 7 (United States-Specific)

SUMMARY TABLE

Referring to Part of the

FOR NATIONAL AUTHORITY USE

Dossier: ONLY:

NAME OF FINISHED PRODUCT:

BMN 270

[figure not shown]
Page:

Volume:

NAME OF ACTIVE INGREDIENT: AAV5-hFVIII-SQ

Reference:

Figure 1: hFVIII-SQ Vector Genome and Encoded Protein

Legend -Note that schematic is not to scale; aa = amino acids; ITR = inverted terminal repeat; HLP = human liver promoter; Kozak = Kozak concensus sequence (GCCACC); SpA = Synthetic poly(A) signal

BMN 270 will be delivered by a single intravenous dose and is designed to achieve stable, potentially life-long expression of active hFVIII in the plasma, synthesized from vector-transduced liver tissue.

BMN 270 is being evaluated in clinical study 270-201, an ongoing first-in-human, phase 1/2 dose escalation study in subjects with severe HA designed to assess the safety and efficacy of BMN 270 at various dose levels (6E12 vg/kg, 2E13 vg/kg, 4E13 vg/kg, 6E13 vg/kg). Specifically, 270-201 explores the relationship of vector dose to the augmentation of residual FVIII activity and whether these levels are sufficient to alter the clinical phenotype. Four-year results from 270-201 and one-year results from 270-301 have demonstrated that following gene transfer, mean and median FVIII activity levels above 15% (15 IU/dL), as measured by a chromogenic substrate assay, are achievable and sustained following a single infusion of 6E13 vg/kg of BMN 270, with an acceptable safety profile. Preliminary results from optional liver biopsies confirm dose-dependent pan-lobular and otherwise healthy liver transduction at 2.7-4.1 years.

The current study is a Phase 3, single-arm, open-label study designed to assess whether, in an expanded sample, BMN 270 can safely alter the clinical phenotype of hemophilia A patients with residual FVIII activity ≤ 1 IU/dL.

OBJECTIVES:

The primary efficacy objective of the study is to:

• Assess the efficacy of BMN 270 defined as FVIII activity, as measured by chromogenic substrate assay, during Weeks 49-52 following intravenous infusion of BMN 270

Page 7

Page 8

NAME OF COMPANY BioMarin Pharmaceutical Inc. [name] [name]	SUMMARY TABLE Referring to Part of the Dossier:	FOR NATIONAL AUTHORITY USE ONLY:
NAME OF FINISHED PRODUCT:	Volume:	
BMN 270	Page:	
NAME OF ACTIVE INGREDIENT: AAV5-hFVIII-SQ	Reference:	

The secondary efficacy objectives of the study are to:

- Assess the impact of BMN 270 on usage of exogenous FVIII replacement therapy in the
 efficacy evaluation period (from Week 5 to last visit by the data cutoff for the 1-year
 analysis, hereafter referred to as "Week 5 to Last Visit")
- Assess the impact of BMN 270 on the number of bleeding episodes requiring exogenous FVIII replacement therapy in the efficacy evaluation period ("Week 5 to Last Visit")

The tertiary efficacy objective of the study is to:

 Assess the impact of BMN 270 on patient-reported outcomes (PROs) at Week 52 of the study compared to baseline

The safety objectives of the study are to:

- Evaluate the safety of BMN 270 during the first 52 weeks following intravenous infusion
- Assess the long-term safety of BMN 270

The exploratory objectives of the liver biopsy substudy are:

- To examine the histopathology of the liver following BMN 270 therapy, including assessing for possible safety findings (eg, fibrosis, fatty liver disease, lymphocytic invasion)
- To quantify FVIII DNA, RNA, and protein expression within hepatocytes
- To determine which forms of rAAV vector DNA are present at the time of biopsy.
- To determine the transduction pattern of BMN 270 in humans (ie, peri-portal hepatocytes, central vein hepatocytes)

The aforementioned study efficacy objectives were achieved through the pre-specified analysis at Week 52 ("1 year analysis") for the study, which was performed in January 2021 after all subjects had been followed for 52 weeks post-BMN 270 infusion (data cutoff date: 16 November 2020). Results from this analysis are intended to support regulatory submissions to EMA and other health authorities outside of FDA.

The FDA has requested BioMarin to submit 2-year safety and efficacy data on all subjects in 270-301 to enable their benefit risk assessment of BMN 270. To fulfill this regulatory requirement, Appendix 2 has been created to specify region-specific study objectives for the United States and the associated endpoints and analyses to achieve them. This analysis ("2-year analysis") will be performed after all subjects have completed the Week 104 visit or have withdrawn from the study.

[figure not shown]
Page 9

NAME OF COMPANY	SUMMARY TABLE	FOR NATIONAL
BioMarin Pharmaceutical Inc.	Referring to Part of the	AUTHORITY USE
[name]	Dossier:	ONLY:
[name]		
	Volume:	
NAME OF FINISHED PRODUCT:		
BMN 270	Page:	
NAME OF ACTIVE INGREDIENT:	Reference:	
AAV5-hFVIII-SQ		

STUDY DESIGN AND PLAN:

This is a Phase 3, single-arm, open-label study in hemophilia A patients with residual FVIII levels ≤1 IU/dL treated continuously with prophylactic exogenous FVIII for a minimum of one year prior to enrollment. Subjects will be enrolled at approximately 60 sites worldwide. Subjects must have high-quality, well-documented historical data available concerning previous bleeding episodes and exogenous FVIII usage over the previous 12 months in order to be eligible to enroll in the study.

Approximately 130 adult subjects with severe HA will receive a 6E13 vg/kg dose of BMN 270 as a single intravenous infusion. Approximately 20 subjects will enroll in the study with at least 12 months of well-documented high-quality historical data concerning previous bleeding episodes and exogenous FVIII usage, while approximately 110 subjects will enroll in the study after having completed approximately 6 months' participation in the BioMarin-sponsored non-interventional study 270-902, in which bleeding and FVIII use data prior to gene therapy will be prospectively collected.

yo = years old, HA = hemophilia A, FVIII = factor VIII, Px = prophylaxis, AAVS = adeno-associated virus, serotype 5. TAb = total antibody, mo = month, wg = vector genomes kg = kilogram, f/u = follow-up

Page 10

NAME OF COMPANY BioMarin Pharmaceutical Inc. [name] [name]	SUMMARY TABLE Referring to Part of the Dossier:	FOR NATIONAL AUTHORITY USE ONLY:
NAME OF FINISHED PRODUCT:	Volume:	
BMN 270	Page:	
NAME OF ACTIVE INGREDIENT: AAV5-hFVIII-SQ	Reference:	

In order to minimize bias in the ongoing study and to assure safe and ethical conduct of the clinical trial, an independent Data Monitoring Committee (DMC), consisting of experts in clinical trials, statistics, and hemophilia, has been convened. The DMC will have sole access during the trial to amalgamated FVIII activity levels, FVIII usage, and bleeding data and review available safety and efficacy (eg, FVIII activity) data during the study on an ongoing basis; they may determine, based on emerging data and the risk/benefit profile, that further enrollment at 6E13 vg/kg should be discontinued in favor of a different dose of BMN 270, not to exceed 6E13 vg/kg. If the DMC recommends a dosing modification, then additional subjects may be enrolled, up to a total of approximately 130 subjects, at the new BMN 270 dose level (regardless of the number of subjects previously enrolled at 6E13 vg/kg).

Two interim analyses were planned, after the first approximately 16 and 20 treated HIV-negative subjects, respectively, completed the Week 26 visit (or have discontinued study participation prior to Week 26). The first interim analysis was performed as planned in May 2019. Based on the interim results and the totality of the data, the secondary interim analysis was deemed unnecessary. The DMC reviewed interim analysis results to assess the efficacy and safety profiles, whether the pre-specified criteria of statistical significance has been achieved, and the risk/benefit ratio of the interventions in the BMN 270 studies based on the totality of the data.

The 1-year analysis for the study was performed after all subjects had been followed for 52 weeks post-BMN 270 infusion. A separate 2-year analysis will also be performed per request from the FDA after all subjects have been followed for 104 weeks post-BMN 270 infusion. After the 1-year and the 2-year analyses, safety and efficacy will then continue to be assessed long-term in all subjects for a total of approximately 5 years.

To avoid breakthrough bleeding, subjects will only discontinue exogenous prophylactic FVIII replacement therapy 4 weeks following infusion of BMN 270. Four weeks represents the time by which endogenous production of FVIII following gene transfer is expected to be efficacious, based on earlier results.

In subjects who experience recurring bleeding episodes, the Investigator and Medical Monitor will discuss whether to resume prior FVIII prophylaxis.

